17.5 Secondary endpoints

17.5.1 Confirmatory secondary endpoints

Provided that IDeg OD is superior to IGlax 300 U/mL OD for the primary endpoint using the primary estimand, the confirmatory secondary endpoints will be tested for superiority of IDeg OD over IGlax 300 U/mL OD using the primary estimand.

The confirmatory secondary endpoints are given below; the order of the endpoints defines the testing sequence. The hierarchical testing strategy will control the family wise type 1 error in the strong sense at 5% (two sided).

1. Basal insulin dose (U) at end of maintenance 2 (up to 88 weeks)
2. Number of nocturnal, severe or BG confirmed symptomatic hypoglycaemic episodes during maintenance 2 (36 weeks)
3. Number of severe hypoglycaemic episodes during maintenance 2 (36 weeks)

The hypoglycaemic endpoints will be analysed with the same analysis method as the primary endpoint and with similar sensitivity analysis.

Basal insulin dose at end of maintenance 2 will be analysed as follows: A basal insulin dose at every titration, maintenance and end of treatment visit mentioned in the flow chart will be

calculated as a mean of the insulin doses in the 7 day period before the visits. These doses will be analysed on log-scale with an MMRM with the factors described in section [17.1](#) and age at baseline and pre-trial insulin dose as covariate. If this model does not converge visits and/or factors will be excluded from the analysis.

Insulin dose will also be analysed with a de-facto estimand, i.e. including using insulin dose collected after premature discontinuation. This is done using a pattern mixture model using multiple imputation to handle missing data. Imputation of missing data at end of trial will be done within the 4 groups of subjects defined by randomised treatment and whether subjects discontinued randomised treatment or not. Missing data within each group will be imputed as follows:

- An analysis of covariance model for insulin dose at week 52 with the factors listed in [17.1](#) (except treatment) and pre-trial insulin dose and age at baseline as covariates will be fitted to the observed data.
- The estimated parameters will be used to impute 1000 values for insulin dose at week 52, creating 1000 complete datasets.

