Data collected after premature treatment discontinuation will not be used when addressing the ontreatment estimand. With the aim of comparing a safety endpoint this estimand is considered the most relevant as it compares the occurrence of a safety endpoint that is caused by the drug during exposure to the drug. The confirmatory endpoints will additionally be investigated with a ITT estimand.

The secondary estimand is the treatment difference between IDeg and IGlar 300 U/mL regardless of whether subjects adhered to the randomised treatment throughout the trial, that is an ITT estimand. For this ITT estimand, data collected after premature discontinuation will be used.

In accordance with guidance⁹ endpoints will be assessed at frequent visits and also for subjects who prematurely discontinue treatment. When an assessment is planned at randomisation visit, this value will be used as baseline value. If this value is missing the last recorded value before randomisation visit will be used. For assessments planned only at screening, the screening values will be used as baseline. If this value is missing, the first recorded visit after screening, but no later than the day of randomisation, will be used.

For patients not initiating maintenance period 2 on treatment a summary table of reasons for treatment discontinuation will be reported.

The severe hypoglycaemia episodes included in the statistical analysis are all events adjudicated with the outcome severe hypoglycaemia.

Laboratory values below the lower limit of quantification (LLOQ) will be set to ½LLOQ. Laboratory values above the upper limit of quantification (ULOQ) will be set to ULOQ+1.

The primary and secondary endpoints will be tested in a hierarchical order using the on-treatment estimand to control the family wise Type I error in the strong sense. Presentation of results from a statistical analysis will include the estimated treatment means as well as estimated mean treatment difference (or ratio) together with the two-sided 95% confidence interval and corresponding two-sided p-value.

In the statistical models explanatory factors will be categorized as follows:

- 1. Treatment: IDeg, IGlar 300 U/mL
- **2.** Pre-trial 0 OADs, 1OAD, \geq 2 OADs
- 3. Region: Europe, North America
- 4. Sex: male, female
- 5. Dosing time: morning, evening

2.2 **Power calculation**

The power is based on the primary objective and the primary endpoint, number of hypoglycaemic episodes during maintenance treatment.

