For the power calculations it is assumed that the true treatment rate ratio (RR) is 0.75 corresponding to a 25% reduction in rate of hypoglycaemia in maintenance period with IDeg OD compared to

Statistical Analysis Plan Trial ID: NN1250-4252 UTN: U1111-1184-8175 EudraCT No.: 2016-002801-20	CONFIDENTIAL	Date: Version: Status: Page:	12 March 2019 3.0 Final 11 of 31	Novo Nordisk
---	--------------	---------------------------------------	---	--------------

IGlar 300 U/mL OD. Sample size is determined based on a negative binomial model with log-offset equal to exposure time in maintenance. The observed rate of severe or BG confirmed symptomatic hypoglycaemia for IDeg is assumed to be 1.8 per patient years of exposure (PYE) and the dispersion parameter in the negative binomial distribution is assumed to be 3.1. Furthermore it is assumed that 4% of subjects will withdraw before starting the maintenance period and therefore have no on-treatment data for the maintenance period. For these 4% the treatment ratio is set to 1. Rate assumptions are based on experience from SWITCH 2 (NN1250-3998), which has similar inclusion criteria. Dispersion parameter assumptions are based on experience from the Degludec phase 3a and 3b program. Assumptions concerning withdrawal are similarly based on actual withdrawal rate of the trial during titration and maintenance 1.

The power equals 79% with the number of randomised subjects and the assumptions above.

			Yearly event rate			
		1.5	1.8	2.0		
RR	Adjusted RR	Primary	Primary	Primary		
0.80	0.812	55%	57%	58%		
0.75	0.765	77%	79%	79%		
0.70	0.718	92%	93%	93%		

 Table 2–1
 Power for the on-treatment estimand for combinations of RR and event rates

The marginal power for detecting a difference between IDeg OD and IGlar 300 U/mL OD with 805 subjects per treatment arm assuming a one-sided t-test at the 2.5% significance level for the confirmatory secondary dose endpoints is shown below. The assumptions are based on data from NN1250-3998 with respect to hypoglycaemic episodes and the phase 3a+b program for the dose-difference.

 Table 2–2
 Marginal power for confirmatory secondary endpoints

		Assumptions			
Endpoint	True ratio	Adjusted RR	CV/ Over dispersion	Rate in IDeg treatment arm	Power
Insulin dose (U)	0.90	0.906	0.65	-	92%
Number of nocturnal, severe or BG confirmed symptomatic hypoglycaemic episodes during maintenance 2	0.7	0.718	3.1	0.55	82%
Number of severe hypoglycaemic episodes during maintenance 2	0.6	0.624	3.1	0.03	31%

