2.4 Primary endpoint

2.4.1 Primary statistical analysis for the on-treatment estimand

The on-treatment estimand will be estimated based on information from maintenance 2 collected when subjects use randomised treatment including a 7-day follow-up period (on-treatment data). Subjects that discontinue randomised treatment during maintenance 2 will contribute with the available on treatment data from maintenance 2. For subjects that discontinue randomised treatment during the titration period or maintenance 1, the number of events in maintenance 2 will be imputed based on data from the same arm from maintenance 2 for subjects that discontinued randomised treatment during maintenance 2. Missing data within each group will be imputed as follows:

- First 1000 samples from the posterior distribution of model parameters will be extracted. The model will be fitted to the on-treatment maintenance 2 data for subjects that discontinued randomised treatment during maintenance 2. This will be done using a Bayes Poisson log-link model dosing time as a factor, age as covariate, and log of exposure time as offset.
- For each sample of model parameters, the total number of hypoglycaemia events for subjects that discontinued randomised treatment in the titration period or maintenance 1 will be imputed as a random number of events from a Poisson distribution using the sampled parameters.

CONFIDENTIAL

Date: Version: Status: Page: 12 March 2019 Novo Nordisk 3.0 Final 13 of 31

Having 1000 complete data sets that have maintenance 2 data for all randomised subjects, the mean treatment ratio will be estimated using a negative binomial model with all the factors described in section 2.1, age as covariate and log exposure time as offset. The estimates and standard deviations will be pooled to one estimate and associated standard deviation using Rubin's formula. From these the 95% confidence intervals for the treatment ratio and the associated p-value will be calculated.

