2.5 Secondary endpoints

2.5.1 Confirmatory secondary endpoints

Provided that IDeg OD is superior to IGlar 300 U/mL OD for the primary endpoint using the ontreatment estimand, the confirmatory secondary endpoints will be tested for superiority of IDeg OD over IGlar 300 U/mL OD using the on-treatment estimand.

The confirmatory secondary endpoints are given below; the order of the endpoints defines the testing sequence. The hierarchical testing strategy will control the family wise type 1 error in the strong sense at 5% (two sided).

Trial ID: NN1250-4252 CONFIDENTIAL Version: 3.0 UTN: U1111-1184-8175 Status: Final EndraCT No : 2016-002801-20 Page: 15 of 31	Statistical Analysis Plan Trial ID: NN1250-4252 UTN: U1111-1184-8175 EudraCT No : 2016-002801-20	CONFIDENTIAL	Date: Version: Status: Page:	12 March 2019 3.0 Final 15 of 31	Novo Nordisk
---	---	--------------	---------------------------------------	---	--------------

- 1. Basal insulin dose (U) at end of maintenance 2 (up to 88 weeks)
- 2. Number of nocturnal, severe or BG confirmed symptomatic hypoglycaemic episodes during maintenance 2 (36 weeks)
- 3. Number of severe hypoglycaemic episodes during maintenance 2 (36 weeks)

The hypoglycaemic endpoints will be analysed with the same analysis method as the primary endpoint including backup strategy and with similar sensitivity analysis.

Basal insulin dose at end of maintenance 2 will be analysed as follows: A basal insulin dose at every titration, maintenance and end of treatment visit mentioned in the flow chart will be calculated as a mean of the insulin doses in the 7 day period before the visits. For the on-treatment estimand these doses will be analysed on log-scale with an MMRM with the factors described in section 2.1 and age at baseline and logarithm of pre-trial insulin dose as covariate, all nested within visit. If this model does not converge visits and/or factors will be excluded from the analysis. Before transforming to log-scale, dose values of 0 will be assigned the value 0.5.

Insulin dose will also be analysed with the ITT estimand, i.e. including insulin dose collected after premature discontinuation. This is done using a pattern mixture model using multiple imputation to handle missing data. Imputation of missing data at end of trial will be done within the 4 groups of subjects defined by randomised treatment and whether subjects discontinued randomised treatment or not. Missing data within each group will be imputed as follows:

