- An analysis of covariance model for insulin dose at visit 93 and 93A with the factors listen in 2.1 (except treatment) and pre-trial insulin dose and age at baseline as covariates will be fitted to the observed data.
- The estimated parameters will be used to impute 1000 values for insulin dose at visit 93/93A, creating 1000 complete datasets.

Having 1000 complete datasets, each of these will be analysed using an analysis of covariance model with all the factors listed in 2.1, pre-trial insulin dose and age at baseline as covariates. The estimates and standard deviations will be pooled to one estimate and associated standard deviation using Rubin's formula. From these the 95% confidence intervals for the treatment ratio and the associated p-value will be calculated.

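### Read literally, the supportive ITT analysis of basal insulin dose imputes from fixed parameter estimates, so its pooled standard error is too small

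*SAP*

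**What the plan says.** SAP 2.5.1 analyses dose twice. The first analysis is a mixed model for repeated measures on log dose, for the on-treatment estimand. The second is a pattern mixture model with multiple imputation, for the ITT estimand. Only the second is at issue.

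The ITT steps are:

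- **Groups.** "Imputation of missing data at end of trial will be done within the 4 groups of subjects defined by randomised treatment" and by whether treatment was discontinued.
- **Model.** "An analysis of covariance model for insulin dose at visit 93 and 93A" is fitted to the observed data with the SAP 2.1 factors except treatment, plus pre-trial dose and age.
- **Imputation.** "The estimated parameters will be used to impute 1000 values for insulin dose at visit 93/93A". Protocol version 3.0, section 17.5.1, has the same step, still at the old time point: "The estimated parameters will be used to impute 1000 values for insulin dose at week 52".
- **Pooling.** The 1000 analyses are "pooled to one estimate and associated standard deviation using Rubin's formula".

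For the hypoglycaemia endpoints, SAP 2.4.1 begins differently: "First 1000 samples from the posterior distribution of model parameters will be extracted". Each data set is then imputed from its own sampled parameters.

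SAP 2.1 states that the primary and secondary endpoints are "tested in a hierarchical order using the on-treatment estimand".

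**The concern.** Rubin's total variance is the average within-imputation variance plus the between-imputation variance. It is valid only if the between-imputation part reflects both sources of uncertainty about a missing value: residual scatter, and not knowing the imputation model exactly. If every data set is generated from the same point estimates, the second source is missing. Raising the number of imputations to 1000 does not restore it.

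The model has about 8 coefficients (intercept, two for OADs, region, sex, dosing time, pre-trial dose, age) and is fitted separately to each arm's discontinued subjects, where observed doses may be few. The error runs one way, towards overstated precision, and it grows as information on discontinued subjects shrinks.

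The ITT analysis is the plan's own check on whether the dose result survives once data after discontinuation are included. It is reported with a 95% interval and a p-value. An interval that is too narrow weakens that check.

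**Working it through.** **1. The plan's own dose figure.** Inputs from SAP 2.2 and Table 2–2: "805 subjects per treatment arm", adjusted ratio 0.906, CV 0.65, one-sided 2.5%.

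- Log-scale SD = sqrt(ln(1 + 0.65²)) = 0.594.
- SE = 0.594 × sqrt(2/805) = 0.0296.
- −ln(0.906)/0.0296 = 0.0987/0.0296 = 3.34, and Φ(3.34 − 1.96) = 91.6%.

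The stated 92% is reproduced. It belongs to the on-treatment test, which uses no imputation, so it does not change. The check also supports 0.594 as the SD for what follows.

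**2. What plug-in imputation omits.** Take N subjects per arm, n discontinued with an observed dose, m discontinued without one, and residual SD σ. Parameter uncertainty should add at least about (m/N)² × σ²/n per arm to the between-imputation variance. Uncertainty in the covariate slopes and in σ adds more.

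Example with N = 805, 105 discontinued, n = 25, m = 80, and σ = 0.594 × sqrt(1 − 0.6²) = 0.475 (correlation 0.6 with pre-trial dose, assumed):

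- Two arms: 2 × (80/805)² × 0.475²/25 = 0.000178.
- The simulated plug-in SE is 0.0254. Adding the omitted part gives sqrt(0.0254² + 0.000178) = 0.0287.
- So even this lower bound puts the plug-in SE about 11% low (0.0254/0.0287 = 0.885).

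**3. Simulation.** Set-up: 805 per arm, log SD 0.594, correlation 0.6, 8-coefficient model within each arm's discontinued group, 40 imputations. The 105 is 13% of 805, the non-completion share assumed in protocol version 2.0, section 17.2. The 48 is 6% of 805, the share implied by the dose ratios in Table 2–2: (0.906 − 0.90)/(1 − 0.90) = 6%, although the text states 4%. The observed counts are assumptions throughout.

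| Discontinued per arm | Observed dose | SE, plug-in | SE, proper draws | Plug-in lower by |
|---|---|---|---|---|
| 105 | 75 | 0.0242 | 0.0246 | under 2% |
| 105 | 50 | 0.0247 | 0.0261 | 5% |
| 105 | 35 | 0.0250 | 0.0283 | 12% |
| 105 | 25 | 0.0254 | 0.0318 | 20% |
| 48 | 30 | 0.0241 | 0.0246 | 2% |
| 48 | 24 | 0.0242 | 0.0253 | 4% |

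Two-sided type I error of the ITT dose comparison, nominal 5%, over repeated runs of the 105-subject set-up:

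| Observed of 105 | Plug-in | Proper draws |
|---|---|---|
| 75 | 5.0% | – |
| 50 | 5.3–6.4% | 5.4% |
| 35 | 7.3–8.2% | 4.9% |
| 25 | 8.7–10.0% | 3.9–4.6% |

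Monte Carlo error is about 0.4–0.7 percentage points, so the result for 50 observed is hardly distinguishable from nominal. With 24 of 48 observed, the rates were 4.8% (plug-in) and 4.0% (proper).

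**4. A second set-up.** All SAP covariates, imputation in all four groups, residual SD 0.594, 100 imputations, 600 trials:

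- 13% discontinued, 31% of them without a dose: 0.0303 against 0.0308 (1.6% low).
- 13% and 50%: 0.0308 against 0.0324 (5% low).
- 20% and 50%: 0.0312 against 0.0332 (6% low).
- 13% and 75%: 0.0317 against 0.0399 (about 20% low; 95% interval coverage 89% against 97%).
- 20% and 75%: 0.0323 against 0.0409 (21% low; coverage 90% against 97%).

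With residual SD 0.40 the SE ratios are almost the same.

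**The case against.** **The wording may be shorthand.** The SAP names the method multiple imputation, pools by Rubin's formula, and never says the parameters are held fixed. Posterior draws are themselves built from the estimates, and standard software draws by default. This stands as a limit: the documents do not prove that the sponsor will plug in. The text nevertheless mentions no draw, SAP 2.4.1 mentions one explicitly, and a programmer following SAP 2.5.1 to the letter would get the wrong standard error.

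**Only a supportive analysis is touched.** This stands in full. Because the section is headed as confirmatory, a reader might infer that a confirmatory test is inflated. The documents do not support that: the hierarchy uses the on-treatment estimand throughout.

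**The large figures rest on weak inputs.** This also stands. The 13% comes from a superseded version with a 52-week design. SAP 3.7 reports few discontinuations in maintenance 2, and protocol 8.1.9 plans to record the basal dose at V93A. Against that, subjects who do not re-consent leave at V54 (protocol 8.1.6) and so have no V93 or V93A dose. Heavy missingness cannot be ruled out.

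**The proper SE is a generous yardstick.** It is somewhat conservative in small groups. Against the estimator's actual variability, the plug-in SE was about 1–3% low with 50 of 105 observed, 7–9% low with 35, and 13% low with 25. This tempers the size but not the direction.

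**Conclusion.** The point holds for the text as written, and only for the ITT analysis of basal insulin dose. Imputing every data set from one set of estimates and pooling with Rubin's formula understates the standard error.

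The effect is small when about half or more of the discontinued subjects have an observed dose, and material when only a quarter to a third of 105 per arm do. A reader might take the upper figures as a forecast for this trial. The documents do not support that, because they give no count of observed V93A doses and no current discontinuation total. The figures also assume normally distributed dose on the log scale; the SAP text for this ITT model reports a ratio but does not name the scale.

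**What to change.** Replace the imputation sentence in SAP 2.5.1 with: *for each of the 1000 imputations, the residual variance and regression coefficients are drawn from their posterior distribution within each group, and missing V93/V93A doses are imputed from the drawn parameters.*

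This brings dose into line with SAP 2.4.1 and needs no new data. If the sponsor already intends a routine that draws parameters, the sentence only records it. The cost is one sentence and a slightly wider ITT interval, which may be mildly conservative where few discontinued subjects have an observed dose.

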2.6 Other endpoints and assessments

2.6.1 Efficacy endpoints

Supportive secondary efficacy endpoints will be summarised descriptively by visits and and supplemented by mean plots of observed values for the continuous endpoints.

2.6.2 Safety endpoints

CONFIDENTIAL

Date: Version: Status: Page:

Adverse events during the total treatment period (titration and maintenance periods)

AEs will be coded using the most recent version of the Medical Dictionary for Regulatory Activities.

A treatment-emergent AE (TEAE) is defined as an event that has onset date on or after the first day of exposure to randomised treatment and no later than 7 days after the last day of randomised treatment, or has onset date before the first day of exposure on randomised treatment and increases in severity during the treatment period and until 7 days after the last drug date. Major adverse cardiovascular events (MACEs, defined as all cardiovascular deaths, non-fatal myocardial infarctions and non-fatal strokes) are considered treatment-emergent until 30 calendar days after the last day of randomised treatment.

AEs are summarised descriptively. AE data will be displayed in terms of the number of subjects with at least one event (N), the percentage of subjects with at least one event (%), the number of events (E) and the event rate per 100 years of exposure (R).

Summaries are presented as an overview including all AEs, serious AEs, number of deaths, AEs by severity, AEs by relation to treatment and AEs leading to treatment discontinuation as summary tables based on system organ class and preferred terms for the following AEs:

- All TEAEs
- All AEs
- All TEAEs during maintenance 2
- Serious TEAEs
- TEAEs possibly or probably related to trial product
- Severe TEAEs
- TEAEs with preferred term that are experienced by at least 5% of the subjects in any treatment arm or by at least 5% of all subjects

Hypoglycaemic episodes

For the definition and classification of hypoglycaemic episodes refer to section 2.7.

Data on treatment-emergent hypoglycaemic episodes are presented in terms of the number of subjects with at least one event (N), the percentage of subjects with at least one event (%), the number of events (E) and the event rate per 100 years of exposure (R).

Separate summaries are made by severity considering severe or BG confirmed symptomatic hypoglycaemic episodes, severe hypoglycaemic episodes, and the Novo Nordisk interpretation of ADA classification of hypoglycaemia from 2018. The summaries are made for all and nocturnal (between 00:01 and 05.59 both inclusive) episodes respectively and for the total treatment period (titration and maintenance periods) and maintenance 2 only (36 weeks).

Trial ID: NN1250-4252 CONFIDENTIAL Version: 3.0 UTN: U1111-1184-8175 CONFIDENTIAL Version: 3.0 EudraCT No.: 2016-002801-20 Page: 17 of 31	Statistical Analysis Plan Trial ID: NN1250-4252 UTN: U1111-1184-8175 EudraCT No.: 2016-002801-20	CONFIDENTIAL	Date: Version: Status: Page:	12 March 2019 3.0 Final 17 of 31	Novo Nordisk
---	---	--------------	---------------------------------------	---	--------------

For both periods, hypoglycaemic episodes during the 7 days treatment-emergent period after last drug day will be included.

The number of severe or BG confirmed symptomatic hypoglycaemic events during total treatment period (up to 88 weeks) will be analysed statistically, addressing both the on-treatment and ITT estimand. Also nocturnal severe or BG confirmed symptomatic hypoglycaemic events as well as severe hypoglycaemic events during total treatment period will be analysed following these procedures.

The on-treatment estimand is estimated based on on-treatment data and a negative binomial model including the factors in section 2.1, age as covariate and the logarithm of the time period in which a hypoglycaemic episode was considered treatment emergent as offset. The model will use log as link function.

The ITT estimand is based on in-trial data. For withdrawn subjects, data after withdrawal will be imputed for a period lasting from the day after withdrawal up until 36 weeks after entering maintenance 2 period, and until 36 weeks after first reconsent of any subject in trial (i.e. until 09NOV2018) for subjects not entering maintenance 2. The imputation will follow the procedure described in section 2.4.1, using all off-treatment data to build the imputation model. Observed and imputed data are summarised by subject, and analysed through a negative binomial model including the factors in section 2.1, age as covariate and the logarithm of the total time period where hypoglycaemic episodes are either observed or imputed as offset. The model will use log as link function. If the imputation model cannot fit or leads to inflate the standard error of the treatment ratio on logscale by more than 15% compared to a negative binomial model fitted to the available on- and off-treatment data during total treatment period without any imputation the analysis will not be performed.

Body weight

Body weight (absolute value and change from baseline) will be summarised descriptively by visit.

Statistical Analysis Plan
Trial ID: NN1250-4252
UTN: U1111-1184-8175
EudraCT No.: 2016-002801-20

CONFIDENTIAL

Date: Version: Status: Page:

